57 primarily to identify modifiable risk factors associated with malnutrition-related morbidity and
58 mortality and assess the effectiveness of targeted nutritional interventions. The secondary objectives
59 include examining variations in nutritional status across cancer types and treatment modalities and
60 exploring how nutritional health interacts with psychological well-being, sleep quality, and physical
61 activity. Participants diagnosed with common malignancies across multiple hospitals undergo
62 baseline nutritional assessments within 48 hours of admission, followed by structured follow-ups at
63 1, 2, 3, 6, and 12 months and then annually for an additional four years to track nutritional changes
64 and key clinical endpoints (Riboli, 2001). Nutritional status, the primary exposure factor, is
65 classified via validated screening tools and dietary intake assessments. Patients are stratified on the
66 basis of malnutrition severity, dietary intake, and nutritional support status, with classifications
67 updated at each follow-up, to evaluate their associations with short- and long-term outcomes (**Fig.**
68 **1**).

[figure not shown]

Fig. 1. The workflow of the NCOM study.

Study Setting & Population

Study sites

The NCOM study was conducted across 11 tertiary hospitals in Xi'an, Shaanxi Province, China.

The participating institutions included Shaanxi Provincial Cancer Hospital; the First Affiliated

Hospital of Xi'an Jiaotong University; the Second Affiliated Hospital of Xi'an Jiaotong University; Shaanxi Provincial People's Hospital; the First Affiliated Hospital of the Fourth Military Medical University; the Second Affiliated Hospital of the Fourth Military Medical University; Shaanxi Provincial Chest Hospital; and the Affiliated Hospital of Northwest University Xi'an No.3 Hospital; Xi'an International Medical Center Hospital; The First Affiliated Hospital of Xi'an Medical University; The Second Affiliated Hospital of Xi'an Medical University.

Recruitment strategy

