The sample size for the NCOM study was determined on the basis of the impact of nutritional status on clinical outcomes in cancer patients, with a two-sided significance level (α) of 0.05 and 80% power ($1 - \beta = 0.80$) (von Elm *et al*, 2007; Arends *et al*, 2017). On the basis of previous studies on nutritional status and cancer outcomes, we assumed a baseline event rate of 20% ($P_1 = 0.50$) in the unexposed group and an expected rate of 24% ($P_2 = 0.40$) in the exposed group (Rasschaert *et al*, 2024). Given that longitudinal oncology cohort studies report attrition rates ranging from 30% to 50% over a multiyear follow-up period (Reeves *et al*, 2007; Schwedhelm *et al*, 2016), the final target sample size for this study was estimated to be approximately 1,538 participants.

Data collection

Data collection followed a standardized protocol across all participating hospitals to ensure consistency and accuracy. The baseline assessments will be conducted within 48 hours of hospital admission, and well-trained researchers will collect information on demographic and clinical data, nutritional status, laboratory biomarkers, quality of life, psychosocial factors, physical activity, sleep status, and knowledge, attitudes, and practices (KAPs). Follow-up assessments will be conducted at predefined intervals to track longitudinal changes in nutritional status and clinical outcomes.

To ensure data reliability, each hospital will designate 1 to 2 trained personnel to be responsible for questionnaires and clinical data recording. At the same time, a supervisor will be appointed to review the integrity of the data and coordinate follow-up work if necessary. All researcher personnel

must complete standardized training and pass competency assessments to ensure consistency in data collection and minimize variations.

Data management will be centralized through the Research Electronic Data Capture (REDCap) system, which ensures data security, accuracy, and accessibility(Harris *et al*, 2009). Standardized, validated measurement tools will be used at each site. Data entry will include built-in validation checks to identify missing values or inconsistencies, with routine audits and cross-site comparisons performed to maintain high data quality and study validity.

Data Content & Assessment Tools

Demographics & Clinical Data

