Upon enrollment, trained personnel will obtain informed consent and record demographic details, including sex, age, marital status, occupation, education, and socioeconomic status. Lifestyle factors such as smoking, alcohol, and tea consumption are documented, given their potential influence on nutritional status and cancer progression(Yuan *et al*, 2023). Medical history, including chronic conditions, previous diagnoses, medication use, and family history of malignancies, will also be recorded to assess genetic predispositions.

Cancer-specific data will be collected at baseline and updated at follow-ups to monitor disease progression and treatment response. This includes pathology-confirmed diagnosis, TNM staging at first diagnosis, and available molecular markers. The tumor burden will be reassessed at each visit, alongside major treatments (surgery, chemotherapy, radiotherapy, targeted therapy, and immunotherapy), with details on the type, duration, and response. Nutritional support, including enteral or parenteral nutrition in the preceding week, will be tracked to evaluate its impact on treatment outcomes.

Karnofsky Performance Status (KPS): The KPS evaluates a patient's ability to perform daily activities, the presence of physical discomfort, and overall performance status, providing a standardized measure of functional impairment(McNair *et al*, 2023).

Nutritional assessments

Nutritional assessments will be conducted via validated screening tools to evaluate nutritional status, risk factors, and dietary intake patterns. Two primary tools and standardized anthropometric

measurements will be employed to assess malnutrition risk and severity:

Subjective Global Assessment (mPG-SGA): The mPG-SGA scoring system consists of five sections: weight loss history, dietary intake changes, symptoms, activity and function levels, and age. Patients' nutritional status will be categorized on the basis of scores as normal (0–2 points), mild malnutrition (3–6 points), and moderate malnutrition (≥ 7 points)(Huo *et al*, 2023a). The version used in this study, mPG-SGAL11, is an adapted and validated version developed for Chinese cancer patients who that incorporates modifications on the basis of nationwide clinical feedback and statistical validation(Fu *et al*, 2022; Huo *et al*, 2023b).

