The nutritional knowledge section evaluates patients' understanding of nutrient composition, dietary recommendations, and the relationship between nutrition and cancer treatment outcomes. The attitude section measures patients' perceptions and beliefs regarding the importance of nutrition in managing cancer-related symptoms and treatment side effects. The practice section assesses

actual dietary behaviors, including food choices, meal frequency, and adherence to nutritional recommendations.

Short-Term & Long-Term Clinical Outcomes

Short-term clinical outcomes will focus on early posthospitalization events within 30 days of admission, providing insights into the immediate impact of nutritional status on patient recovery and complications. These outcomes will include 30-day survival status, intensive care unit (ICU) admissions, length of stay, and total hospitalization costs, with a specific breakdown of nutrition-related expenses, such as enteral and parenteral nutrition. Additionally, changes in body weight within 30 days of hospitalization will be monitored as a key indicator of early nutritional deterioration. The incidence of complications, including infections, malnutrition, and drug-related adverse effects, will be systematically recorded to assess treatment-related risks. These measures provide critical data on the role of nutritional status in influencing short-term recovery, treatment complications, and overall resource utilization.

Long-term clinical outcomes will be assessed through regular survival tracking at each scheduled follow-up visit. Patient survival status will be documented to analyze survival trends over time and the potential impact of nutritional interventions on overall prognosis. The follow-up evaluations will categorize patients as alive and disease-free, alive with disease progression, or deceased, with the cause of death recorded.

Adverse Event Recording

Adverse events (AEs) will be systematically recorded and monitored throughout the study to ensure patient safety and data integrity. AEs are defined as any unfavorable or unintended medical occurrence, regardless of their direct relationship with nutritional interventions or treatment. These may include treatment-related complications, gastrointestinal distress, metabolic imbalances, infections, allergic reactions, or other unexpected health changes.

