Nutrition support in and out of hospital Nutrition support	√	√	√	√	√	√	√
Laboratory biomarkers	√	√	√	√	√	√	√
EORTC QLQ-C30	√	√	√	√	√	√	√
HADS	√	√	√	√	√	√	√
PSQI	√	√	√	√	√	√	√
Leisure-time physical activity levels	√	√	√	√	√	√	√
KAP Questionnaire	√				√	√	√
Short-Term Clinical Outcome		√	√	√	√	√	√
Long-term clinical outcomes		√	√	√	√	√	√
Adverse Event Recording	√	√	√	√	√	√	√

299 **Table 1.** Follow-up schedule. SV: screening visit; KPS: Karnofsky Performance Status; mPG-SGA:
 300 Subjective Global Assessment; NRS-2002: Nutritional Risk Screening 2002; SDSAT: Simple Diet Self-
 301 Assessment Tool; EORTC QLQ-C30: European Organization for Research and Treatment of Cancer

Quality of Life Questionnaire C30; HADS: Hospital Anxiety and Depression Scale; PSQI: Pittsburgh Sleep Quality Index; KAP : Knowledge, Attitude, and Practice.

Statistical analysis plan

Baseline characteristics are summarized as the means \pm standard deviations (SDs) for normally distributed variables, medians with interquartile ranges (IQRs) for skewed data, and percentages for categorical variables. For group comparisons (e.g., normal vs. mild malnutrition vs. moderate malnutrition patients), independent t tests or Mann–Whitney U tests were used for continuous variables, and chi–square tests or Fisher’s exact tests were used for categorical data.

The primary outcome analysis will apply multivariate regression models, adjusting for age, sex, cancer stage, treatment modality, socioeconomic status, and baseline Karnofsky Performance Status (KPS). Logistic regression was used to assess binary outcomes (e.g., nutritional risk, survival), whereas linear regression was used to evaluate continuous variables (e.g., BMI changes, weight loss percentage). To account for repeated measures, generalized estimating equations (GEEs) model longitudinal variations in nutritional status, biomarkers, and quality of life.

For survival analysis, Kaplan–Meier curves were used to estimate overall survival (OS) and progression-free survival (PFS), with log-rank tests used to compare groups. Cox proportional hazards models were used to explore the associations between nutritional status and survival outcomes, incorporating time-dependent covariates where applicable.

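### Malnutrition is listed as a 30-day complication although malnutrition severity at admission is the primary exposure, so that item is circular when compared across the malnutrition groups

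*Protocol*

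**What the plan says.** **Exposure.** The Study design section of the protocol introduces "Nutritional status, the primary exposure factor, is" classified by screening tools and dietary assessment. Patients are grouped on the "basis of malnutrition severity, dietary intake, and nutritional support status, with classifications" that are "updated at each follow-up, to evaluate their associations with short- and long-term outcomes". On timing, the Data collection section says: "The baseline assessments will be conducted within 48 hours of hospital admission". The Nutritional assessments section sets the mPG-SGA classes: normal (0-2 points), then "mild malnutrition (3–6 points), and moderate malnutrition" (7 points or more). The Statistical analysis plan section of the protocol gives these three classes as its example of a group comparison.

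**Outcome.** The Short-Term & Long-Term Clinical Outcomes section limits short-term outcomes to 30 days from admission. Among them it lists "The incidence of complications, including infections, malnutrition, and drug-related adverse effects". The same paragraph ends by saying that these measures inform on how nutritional status influences recovery and treatment complications.

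**Not stated.** The protocol does not say whether malnutrition as a complication means presence, new onset or worsening. It does not say who is at risk of it, or whether complications are pooled or analysed singly.

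**The concern.** An outcome used to show the effect of an exposure should not contain the exposure. Here the grouping variable is malnutrition class at admission, and one of the events compared is malnutrition up to 30 days later. The result for that item depends mainly on the counting rule and says little about the consequences of being malnourished.

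The direction of the error changes with the rule. A state definition makes baseline malnutrition look harmful, and a new-onset definition over all patients makes it look protective. If the item is also pooled with infections and drug-related adverse effects, it can mask or imitate a real association with those events, which are the ones of clinical interest.

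**Working it through.** **Plan's own figure.** There is none to reproduce. The protocol gives no 30-day rate for complications, for new malnutrition or for persistence of malnutrition, and its sample size does not bear on this point. All rates below are assumptions.

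**Inputs (assumed).**
- c = risk of any other complication, 10-30%, equal in both groups (no true effect).
- p = proportion of patients malnourished at baseline who are still malnourished at 30 days, 50-100%.
- i = proportion of patients normal at baseline who become malnourished by 30 days, 10-20%.
- Malnutrition and other complications are independent.
- Mild and moderate are combined as exposed; normal is unexposed.

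**Step 1: the malnutrition item alone.**
- State: risk ratio = p / i, from 0.50/0.20 = 2.5 to 1.00/0.10 = 10.
- New onset over all patients: exposed risk = 0, because these patients already have the condition, so the ratio is 0 whatever the value of i.
- Infections and drug-related adverse effects, analysed separately, are untouched.

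**Step 2: a pooled any-complication endpoint (an assumption; the protocol defines none).** Risk = 1 - (1 - c)(1 - m), where m is the risk of meeting the malnutrition item.

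*State:* m = p in the exposed, m = i in the unexposed.
- Lowest ratio (c = 0.30, p = 0.50, i = 0.20): (1 - 0.70 × 0.50) / (1 - 0.70 × 0.80) = 0.65/0.44 = 1.5.
- Middle (c = 0.20, p = 0.80, i = 0.10): 0.84/0.28 = 3.0.
- Highest (c = 0.10, p = 1.00, i = 0.10): 1.00/(1 - 0.90 × 0.90) = 1.00/0.19 = 5.3.

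*New onset over all patients:* m = 0 in the exposed, m = i in the unexposed.
- Lowest (c = 0.10, i = 0.20): 0.10/(1 - 0.90 × 0.80) = 0.10/0.28 = 0.36.
- Middle (c = 0.20, i = 0.10): 0.20/0.28 = 0.71.
- Highest (c = 0.30, i = 0.10): 0.30/(1 - 0.70 × 0.90) = 0.30/0.37 = 0.81.

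The true ratio is 1.0 in every case.

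**Step 3: with a true effect.** Suppose other complications occur in 20% of unexposed and 24% of exposed patients, a true ratio of 1.20. These percentages are borrowed from the Sample size section for illustration only; that section gives conflicting symbols (0.50 and 0.40) for the same rates. Under new onset with i = 5%, the unexposed risk is 1 - 0.80 × 0.95 = 0.24 and the ratio is 0.24/0.24 = 1.00. A 5% incidence cancels the effect, and a higher one reverses it: at i = 10%, 0.24/0.28 = 0.86.

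**Step 4: which parts depend on the assumptions.** The new-onset direction follows from the definition for any i above zero when c is equal in both groups. The upward direction of the state reading needs p to exceed i. The sizes depend on all the assumed rates.

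**Step 5: worsening as a third reading.** By mPG-SGA class, a mild patient can become moderate, but a patient in the top class (7 points or more) cannot move up. A definition based on change in score would not have this ceiling.

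**Step 6: malnutrition removed.** The pooled ratio is c/c = 1.00 in Step 2 and 0.24/0.20 = 1.20 in Step 3.

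**The case against.** The strongest reply has four parts.

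*The protocol defines no pooled complication endpoint.* This stands. The ratios in Step 2 apply only if complications are pooled. A reader might infer that the whole comparison of complications by nutritional status is biased as planned; the documents do not support that. Analysed one by one, infections and drug-related adverse effects are unaffected and only the malnutrition item is circular.

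*The word incidence points to new events, and incidence is normally taken among those at risk.* This stands in part. It makes the state reading, and with it the figure of 5.3, the less natural one. An at-risk denominator, or worsening defined on the score, would avoid the bias. The protocol adopts neither, and it presents the complications as a measure of the influence of nutritional status.

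*A separate statistical analysis plan could settle the definition.* It could settle definition, denominator and pooling, and their absence is not the complaint. The complaint is that the protocol itself lists the exposure among the outcomes.

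*Nutrition is legitimately an outcome elsewhere in this study.* This stands. A reader might infer that the regression outcomes, "binary outcomes (e.g., nutritional risk, survival" among them, and weight loss percentage are circular as well, since the mPG-SGA is built from "weight loss history, dietary intake changes, symptoms, activity and function levels, and age". The documents do not show this. The analysis section does not make nutritional status the predictor in those models, and a secondary objective examines how nutritional status varies by cancer type and treatment. Weight loss history at admission is also a different quantity from weight change during the following 30 days.

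**Conclusion.** The point holds for the malnutrition item. Listed among complications to be related to nutritional status, it puts the exposure on both sides whenever patients are grouped by malnutrition class, and nothing in the protocol restricts it to patients at risk or sets it apart.

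As a state it favours the normal group, provided persistence exceeds incidence; as new onset over all patients it favours the malnourished groups by definition. A pooled endpoint would carry the bias with it, and the ranges in Step 2 show that it could be large. They are illustrations of an endpoint the protocol does not define, at assumed rates, and are not estimates for this study. The matter is worth correcting because the correction is simple; it does not undermine the other short-term outcomes.

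**What to change.** 1. In the Short-Term & Long-Term Clinical Outcomes section, state that where malnutrition status (mPG-SGA or NRS-2002 category) is the exposure, the complication outcome consists of infections and drug-related adverse effects and excludes malnutrition. For this comparison, take the exposure from the 48-hour assessment: classes are updated at each follow-up, and the 1-month update coincides with the end of the 30-day window.
2. Report new-onset malnutrition separately, only in patients classed as normal at the 48-hour assessment, as an outcome of the models of risk factors for malnutrition.
3. Say whether the remaining complications are pooled or analysed singly.

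The restriction need not extend to dietary intake or nutritional support as exposures, since malnutrition is not the same variable as either.

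**Cost.** A few sentences and somewhat fewer complication events. No new data are needed: Table 1 already schedules the mPG-SGA and NRS-2002 at the screening visit and at month 1.

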Eligible patients will be recruited by clinical medical staff. Recruitment will primarily occur through direct physician referrals during oncology consultations, supplemented by promotional materials in hospitals, such as posters, brochures, and electronic notices. Patients and their families who learn about the study through these materials can also self-refer by contacting the research team. The screening process consists of two steps. The first screening visit (SV1) is conducted remotely via online consultation or phone call to assess basic eligibility, including willingness to participate and key exclusion factors such as pregnancy or concurrent trial participation. Informed consent is obtained at this stage. Patients who pass SV1 will proceed to the second screening visit (SV2), which will be conducted onsite at each hospital. During SV2, medical records will be reviewed, and clinical assessments will be performed to confirm whether patients meet the inclusion and exclusion criteria. Only patients who meet all the criteria will be formally enrolled.

Inclusion criteria

- a. Age \geq 18 years.
- b. Histologically confirmed diagnosis of malignancy.
- c. Patients are scheduled to receive oncologic treatment, including surgery, chemotherapy, radiotherapy, or a combination.
- d. Mentally competent and able to provide informed consent.
- e. Willingness to participate in follow-up assessments
- f. Patients with multiple hospital admissions may be included in repeat assessments, with each admission counted as an independent case.

Exclusion criteria

Patients were excluded if they met any of the following criteria:

- a. Severe comorbidities that may interfere with participation (e.g., end-stage liver/kidney disease or severe cardiac failure).
- b. Patients with HIV/AIDS.
- c. Prior organ transplantation recipients.
- d. Expected survival of less than 6 months.
- e. Pregnant patients.
- f. Patients currently participating in another interventional clinical trial.

Sample size

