At each follow-up visit, trained personnel will actively assess AEs by reviewing medical records and laboratory findings, while participants will be encouraged to self-report symptoms between visits. Serious adverse events (SAEs), including hospitalization, prolonged disability, or life-threatening conditions, will be reported following institutional and ethical guidelines.

All AEs and SAEs are classified by severity, duration, and potential causality, with standardized

procedures for data entry, review, and risk assessment. Necessary medical interventions or protocol adjustments will be implemented as needed. This structured monitoring system will increase patient safety, reduce risks, and provide insights into the impact of nutritional interventions on clinical outcomes.

Follow-up assessments and data collection timeline

Follow-up assessments will be conducted at predefined intervals to track longitudinal changes in nutritional status, clinical outcomes, and survival trends. In the first year, participants will be closely monitored at 1, 2, 3, 6, and 12 months to assess early nutritional changes and treatment-related complications. Afterward, annual follow-ups will continue for an additional four years or until death or loss to follow-up, with a focus on survival status and disease progression. In-person hospital visits will be prioritized for follow-up to ensure a comprehensive evaluation of nutritional status, clinical outcomes, and quality of life (**Table 1**). If in-person visits are not feasible, telephone follow-ups serve as an alternative. Research personnel will document each follow-up attempt, including the method of contact, date, and details of the interaction. To minimize loss to follow-up, participants missing scheduled visits were contacted up to three times via phone calls or text messages. If a participant remains unreachable after three attempts, they will be classified as lost to follow-up, and their last recorded assessment will be used for analysis. Any known reasons for withdrawal, relocation, or health deterioration will be documented to ensure data transparency and completeness.

Variable	SV	Folllow-up						
		1 st month	2 nd month	3 rd month	6 th month	12 th month	Annually follow-up for another 4 years	

Demographics & Clinical Data	√						
KPS Scoring	√	√	√	√	√	√	√
mPG-SGA	√	√	√	√	√	√	√
NRS2002	√	√	√	√	√	√	√
Standardized anthropometric measurements	√	√	√	√	√	√	√
SDSAT	√	√	√	√	√	√	√

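### The follow-up status list has no code for a patient alive with stable or responding disease, so such patients must be miscoded or left uncoded, and PFS is at risk if it uses this code

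*Protocol*

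**What the plan says.** The Protocol's section on Short-Term & Long-Term Clinical Outcomes sets the status recorded at each scheduled follow-up: "The follow-up evaluations will categorize patients as alive and disease-free, alive with disease progression, or deceased, with the cause of death recorded". Table 1 ticks long-term outcomes at every follow-up from month 1 onward.

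Two inclusion criteria decide who is followed: "Histologically confirmed diagnosis of malignancy" and "Patients are scheduled to receive oncologic treatment, including surgery, chemotherapy, radiotherapy, or a combination". Neither they nor the exclusion criteria restrict stage or resectability. Expected survival under 6 months is an exclusion, but that still leaves patients with advanced disease eligible.

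The Statistical analysis plan section of the Protocol names PFS as an endpoint: "Kaplan–Meier curves were used to estimate overall survival (OS) and progression-free survival (PFS"; groups are then compared by log-rank tests. It does not say which recorded item supplies the progression event.

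Under Demographics & Clinical Data there is a second possible source: "Cancer-specific data will be collected at baseline and updated at follow-ups to monitor disease progression and treatment response". The same paragraph adds: "The tumor burden will be reassessed at each visit, alongside major treatments", with response among the treatment details recorded. Table 1, however, ticks the Demographics & Clinical Data row at the screening visit only and has no separate row for tumour assessment.

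**The concern.** A status list used at every follow-up should give each patient exactly one correct code. This one does so for patients with no remaining disease, for those who have progressed, and for those who have died. It has no code for someone alive with disease that has not progressed. That is an ordinary state for a patient still under chemotherapy or radiotherapy at months 1, 2 or 3.

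Staff who follow the stated rule must put such a patient in a category that is untrue or leave the item blank. The Protocol gives no coding rule, so the 11 hospitals may well solve the problem differently. Two things are at stake: the meaning of the disease-free category, and PFS if it is taken from this code. A later analysis plan could not recover the state from this item, because the item does not record it.

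**Working it through.** The Protocol states no PFS rate, event count or PFS power, so there is no figure of its own to reproduce. There are two checks.

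**Check 1: is the list exhaustive?**

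| State at a follow-up visit | Code available |
|---|---|
| Alive, no evidence of disease | Yes |
| Alive, disease present, stable or responding | None |
| Alive, disease progressed | Yes |
| Dead | Yes |

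One of the three living states has no code. The inclusion criteria admit patients who will be in that state, and Table 1 asks for the status from month 1.

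**Check 2: what does each workaround do at a single visit?**

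Inputs, all assumed because the Protocol gives none:
- *e*, the true share with progression or death: 20% or 40%.
- *s*, the share alive with stable or responding disease: 10%, 30% or 50%.
- *f*, the fraction of *s* coded as progressed: from 0 to 1, the rest being coded disease-free.

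Formulas:
- True event-free share = 1 − *e*.
- True disease-free share = 1 − *e* − *s*.
- Recorded event-free share = 1 − *e* − *f* × *s*.
- Recorded disease-free share = the same expression, because the only other living code is progression.
- If these patients are left uncoded and dropped, recorded event-free share = (1 − *e* − *s*) / (1 − *s*).

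Results for the event-free share, which is what PFS needs:

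| *e* | *s* | True | All coded disease-free (*f* = 0) | Half coded progressed (*f* = 0.5) | All coded progressed (*f* = 1) | Uncoded and dropped |
|---|---|---|---|---|---|---|
| 20% | 10% | 80% | 80% | 75% | 70% | 77.8% |
| 20% | 30% | 80% | 80% | 65% | 50% | 71.4% |
| 20% | 50% | 80% | 80% | 55% | 30% | 60.0% |
| 40% | 10% | 60% | 60% | 55% | 50% | 55.6% |
| 40% | 30% | 60% | 60% | 45% | 30% | 42.9% |
| 40% | 50% | 60% | 60% | 35% | 10% | 20.0% |

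Example for the last column: with *e* = 20% and *s* = 30%, (1 − 0.20 − 0.30) / (1 − 0.30) = 0.50 / 0.70 = 71.4%.

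The disease-free category moves the opposite way. With *e* = 20% and *f* = 0, the recorded disease-free share is 80%, while the true share is 70%, 50% or 30% for *s* = 10%, 30% or 50%. So when every patient is given one of the three codes, a share *s* is always misplaced. The workaround only decides whether the disease-free share or the progression share absorbs it.

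These are single-visit shares, meant to show the range. They are not a prediction of the study's Kaplan–Meier curve.

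**The case against.** The strongest reply is that PFS may not use this code at all. The Protocol presents the status list as part of survival tracking, and nowhere says that PFS is derived from it. The Demographics & Clinical Data section promises tumour burden and treatment response at follow-up, which would separate response from progression. Even if the code were used, PFS only distinguishes progression or death from neither, so a stable patient coded disease-free is correctly event-free. The data-capture form is not shown, and its checks for missing or inconsistent entries might catch some cases. PFS is not designated as the primary outcome, and overall survival is untouched.

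Most of this stands, and it limits the point. It does not remove it. The second source is not clearly scheduled: Table 1 ticks clinical data at screening only, and telephone contact may replace a visit. If the second source is collected as the text says, it will disagree with the status code for every stable or responding patient. Checks for blanks cannot supply a category that does not exist.

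Three stronger readings are tempting but not supported:
- *The planned PFS will be wrong.* This needs both that PFS is taken from this code and that patients are coded as progressed or dropped. The Protocol states neither.
- *The comparison between nutritional groups will be biased.* Coding habits could differ with cancer type or hospital, but nothing in the Protocol shows that they differ by nutritional status.
- *Progression will be dated late because visits become yearly after month 12.* The Protocol says that "annual follow-ups will continue for an additional four years", but it never says that the visit date serves as the progression date. Dating and censoring rules are commonly left to an analysis plan.

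**Conclusion.** The point holds as a defect in a stated data-collection rule. The three-way status list is not exhaustive, and eligible patients will fall outside it from month 1. Following the rule exactly records them falsely or not at all.

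The consequence for PFS is a risk, not a certainty. If PFS is taken from this code, the error in the event-free proportion at a visit is zero when these patients are coded disease-free, and equals their full share when all are coded as progressed. Dropping them lowers the estimate by a smaller amount: about 2 to 20 percentage points at an assumed 20% true event share, and about 4 to 40 at 40%, for shares of 10% to 50%. Those shares are illustrations, since the Protocol gives no stage mix or response rates. If PFS is taken from tumour-burden and response data instead, this gap does not affect it, provided those data are collected at follow-up. The disease-free category is false wherever it is used to hold these patients.

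**What to change.** 1. Add a fourth follow-up category: *alive with disease, not progressed (stable or responding)*. With it, every patient whose disease state is known can be coded truthfully, and the event-free share recorded at a visit equals the true share under any values in the working above.
2. State in one sentence whether PFS is derived from this status or from the tumour-burden and response data.
3. Reconcile the Demographics & Clinical Data text, which updates cancer data and tumour burden at follow-up, with Table 1, which ticks clinical data at screening only.

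The cost is one extra option in the data-capture form, a sentence or two of text and a correction to Table 1 or to the section it conflicts with. No sample size, treatment or visit changes. If follow-up statuses have already been entered under the three-way list, records of living patients would need to be rechecked against their clinical notes. That becomes harder with time, so the change should be made early.
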